3.6 Register and EMR data

Register data will be obtained via Statistics Denmark and include variables from several registers, including the following population registries: The National Population Registry, the Civil Registration System, the Education Registry, the Income Registry and the Address Registry, and the following health registries: the National Patient Registry, the National Prescription Registry, the Hospital Medicine Registry, and the Health Insurance Registry. A data extraction agreement with Statistics Denmark has been made and is currently being processed.

Key population variables extracted for both study groups include, but are not limited to, gender, age, education, occupation and income (socioeconomic status), as well as household composition, all encounters with the health care system in the survey period (e.g., if the participant has been admitted to the hospital with a ketoacidosis), redeemed prescriptions from hospitals and pharmacies, and distance to health care services from private address.

Diabetes-specific clinical outcomes in both study groups will be extracted from registers, and from survey respondents' EMRs. Register-extracted outcomes include all blood and urine test measures taken at the annual 'check-up', including HbA1c, hemoglobin, eGFR, UACR, cholesterol total, HDL, LDL, VLDL, triglycerides, diabetes-related complications and other somatic and psychiatric comorbidities. EMR-extracted outcomes (available only for the survey group) include BMI, blood pressure and hypoglycemia awareness status, which are not tracked in national registers.

3.7 Data analysis

The overall data analysis approach is based on descriptive, non-parametric and parametric statistical methods. Descriptive statistics will include amounts/counts (n), shares (%), means and variable distributions (standard deviations and percentiles). Non-parametric hypothesis tests will include the Chi-squared test, Fisher's exact test and Wilcoxon rank test depending on variable distributions. Parametric hypothesis tests will center on Student's unpaired and paired t-tests as well as general and generalized regression analyses. Model error structures will depend on the specific objective but, in general, take the following form:

$$Y_i = \beta_0 + \beta_1 X_{1i} + \beta_2 X_{2i} + \dots + \beta_n X_{ni} + e_i$$

where Y is the dependent variable (e.g., HbA1c) for individual i , β_n is the effect on Y_i given X_n , where X_n indicates demographic, socioeconomic, behavioral and psychosocial factors, and e_i indicates residual error (i.e., unexplained variance).

Furthermore, quasi-experimental procedures such as propensity score or coarsened exact matching and machine-learning algorithms such as random forest will be employed to maximize data usage and to foster meaningful comparisons within and between the two study groups.

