3.1 Study groups/cohorts

The study population consists of two groups/cohorts:

1. Steno Tech Survey Respondents: A cohort of individuals with type 1 diabetes treated with CSII at either SDCC or NOH participating in the Steno Tech Survey.
2. General Type 1 Diabetes Population: A cohort consisting of the entire population of people with type 1 diabetes in Denmark not included in the Steno Tech Survey cohort (ca. 25.000 individuals).

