3.8 Ethics

The study was approved by the Danish Data Protection Agency (P-2019-812) and exempted from review by the Capital Region of Denmark's Research Ethics Committee (19080899). The study was also registered on ClinicalTrials.gov (NCT04311164).

4. Results

Data collection for this study is currently in progress. Survey data collection was initiated on May 15, 2020 and completed on October 15, 2020. In total, 770 individuals responded to the survey. EMR and register data are currently being extracted and prepared for merge with survey data by Statistics Denmark.

5. References

1. Diabetes C, Complications Trial Research G, Nathan DM, Genuth S, Lachin J, Cleary P, et al. The effect of intensive treatment of diabetes on the development and progression of long-term complications in insulin-dependent diabetes mellitus. *N Engl J Med* 1993; **329**: 977-986.
4. Dansk Voksen Diabetes Database, Dansk Register for Børne- og Ungdomsdiabetes, Landsdækkende klinisk kvalitetsdatabase for screening af diabetisk retinopati og maculopati, Regionernes Kliniske Kvalitetsudviklingsprogram. Dansk Diabetes Database - National årsrapport 2017/2018. Copenhagen, Denmark 2018.
6. Franklin V. Influences on Technology Use and Efficacy in Type 1 Diabetes. *J Diabetes Sci Technol* 2016; **10**: 647-655.
8. Pickup JC. Is insulin pump therapy effective in Type 1 diabetes? *Diabet Med* 2019; **36**: 269-278.

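### Section 3.7 names Student's unpaired t-test and no unequal-variance method; for very unequal groups, Welch's test and robust standard errors are safer at almost no cost

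*Combined protocol and SAP*

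**What the plan says.** Section 3.7 (Data analysis) describes the parametric methods in one sentence: "Parametric hypothesis tests will center on Student's unpaired and paired t-tests as well as general and generalized regression analyses". For regression it adds that "Model error structures will depend on the specific objective", which leaves the variance assumption open. The non-parametric list ends with the "Wilcoxon rank test depending on variable distributions". The last paragraph of 3.7 adds propensity score or coarsened exact matching and machine learning, in order to reach "meaningful comparisons within and between the two study groups".

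The two groups differ greatly in size. Section 3.1 puts the general type 1 diabetes cohort at "ca. 25.000 individuals" (the point is a thousands separator). Section 4 (Results) reports: "In total, 770 individuals responded to the survey". Section 3.6 shows that continuous outcomes exist on both sides: "Diabetes-specific clinical outcomes in both study groups will be extracted from registers". They include HbA1c, eGFR and lipids.

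No section names Welch's test, an unequal-variance option or a robust standard error. No section states an alpha level, a matching ratio or an SD for any outcome.

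**The concern.** Student's unpaired test estimates one common variance. With 770 against 25,000, that estimate is almost entirely the variance of the large cohort. The uncertainty in the difference comes mainly from the small one: with equal SDs, the 770 contribute (1/770)/(1/770 + 1/25,000) = 97% of the sampling variance. The test therefore takes its variance from one group and its sampling error from the other. If the SDs differ, confidence intervals and p-values miss their nominal level, and a larger sample at the same size ratio does not help.

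Equal SDs cannot be taken for granted. The respondents are adult pump users at two centres who are fluent in Danish (sections 3.1 and 3.2). The comparison cohort is everyone else in the country with type 1 diabetes, with no age or treatment limit stated. The direction is unknown. If respondents vary less, the test is conservative and loses some power. If they vary more, false positives exceed the nominal level. The same mechanism acts, on a smaller scale, on unpaired tests of unequal subgroups within the 770.

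**Working it through.** The plan gives no sample-size, power or alpha figure, so there is nothing of its own to reproduce.

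**Inputs from the documents.** n1 = 770 (section 4); n2 = 25,000 (section 3.1, approximate).

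**Assumptions not in the documents.** Two-sided 5% level; unmatched comparison; SD of the larger group set to 1; SD of the smaller group = r, varied from 0.8 to 1.25.

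**Formulas.**

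- SE_pooled = sqrt{[(n1−1)r² + (n2−1)]/(n1+n2−2)} × sqrt(1/n1 + 1/n2)
- SE_true = sqrt(r²/n1 + 1/n2)
- k = SE_pooled/SE_true
- actual type I error = 2 × [1 − Φ(1.96k)]

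**Worked case, r = 0.8.** The pooled variance is (769 × 0.64 + 24,999)/25,768 = 0.9893. Then SE_pooled = sqrt(0.9893 × 0.0013387) = 0.0364. SE_true = sqrt(0.64/770 + 1/25,000) = 0.0295. So k = 1.233 and the type I error is 2 × [1 − Φ(2.417)] = 1.6%.

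**Results at 770 vs 25,000.**

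| r | k | Type I error, Student |
|---|---|---|
| 0.8 | 1.233 | 1.6% |
| 0.9 | 1.104 | 3.1% |
| 1.0 | 1.000 | 5.0% |
| 1.1 | 0.914 | 7.3% |
| 1.25 | 0.811 | 11.2% |

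**Simulation** (normal data, 400,000 runs), Student / Welch: 1.5% / 5.0% at r = 0.8 and 11.2% / 5.0% at r = 1.25.

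**Loss on the conservative side, r = 0.8.** The effect detectable with 80% power is (1.96 + 0.842) × 0.0295 = 0.083 SD with Welch, against (1.96 × 1.233 + 0.842) × 0.0295 = 0.096 SD with Student.

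**Fewer controls.** With two controls per respondent (770 vs 1,540), the error is 3.5% at r = 0.8 and 6.9% at r = 1.25. At 770 vs 770, k = 1 for any r and the error is 5.0%.

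**Within respondents.** An assumed 77 vs 693 split gives 1.9% (small-to-large SD ratio 0.8) to 10.1% (1.25). Welch holds 5.0% at both ends in simulation.

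**Regression.** With a cohort term and one covariate at 770 vs 25,000 (5,000 runs, Monte Carlo SE 0.2 to 0.5 points), constant-variance least squares / HC3 gives 1.6% / 5.4% (r = 0.8), 4.8% / 5.0% (1.0) and 11.5% / 5.0% (1.25).

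**Matched data.** In 770 sets of 1:5 with equal SDs (6,000 runs, Monte Carlo SE 0.1 to 0.3 points), Student / Welch / matched-set standard error gives 2.7% / 2.8% / 4.5% at an assumed within-set correlation of 0.2, and 1.1% / 1.2% / 5.1% at 0.4. Welch is therefore not the remedy once sets are matched.

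**Price of Welch with equal SDs.** At 770 vs 25,000 it has about 817 df. The critical value is 1.9629 against 1.9601, a ratio of 1.0014. At 77 vs 693 the interval is about 1.1% wider.

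**Comparison with bias.** With equal SDs, SE = sqrt(1/770 + 1/25,000) = 0.0366. A residual bias of 0.05 SD then gives a mean z of 0.05/0.0366 = 1.37 and a rejection rate of about 28%.

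**The case against.** The strongest reply is that no planned analysis is shown to be affected. Section 3.7 does not say that a t-test will compare the two cohorts. The sentence on comparing them concerns matching and machine learning, and at 1:1 the error is nil. This is correct, and it is why the point is conditional. But 3.7 neither fixes a matching ratio nor limits tests to matched data, and unpaired tests within the respondents are exposed either way.

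A second reply is that the plan keeps its options open through flexible error structures, generalized regression and Wilcoxon. That makes this an unspecified choice in the regressions and not a contradiction. It does not commit the analyst to a valid variance, and Wilcoxon is not an unequal-variance test of means.

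Third, the size rests on assumed SD ratios. At ratios of 0.95 to 1.05 the error is only 4.0% to 6.1%, and below 1 the test merely errs on the safe side. This stands.

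Fourth, in exploratory work on such different cohorts, exact equality of unmatched means is hardly a credible null, and confounding or non-response can outweigh the standard error: the 28% from a 0.05 SD bias exceeds the worst case tabulated. This also stands, and it caps the importance of the point. It is no reason to keep the less reliable standard error.

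Finally, a model with the survey's psychosocial scales can be fitted only in the 770, so a remedy limited to two-cohort regressions does not reach it. That is fair; the regression check here covers the two-cohort case only.

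**Conclusion.** The point holds as a minor, cheap improvement. The plan names a pooled-variance test where an unequal-variance test is at least as reliable, for groups that may differ in size by a factor of about 32 (25,000/770). For an unmatched comparison at an assumed two-sided 5% level, the type I error would lie between 1.6% and 11.2% for SD ratios from 0.8 to 1.25. The range narrows to 3.5% to 6.9% with two controls per respondent, and the error vanishes at 1:1. Whether the SDs differ, and in which direction, cannot be told from the documents. A corrected standard error would not make a confounded contrast interpretable.

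**What to change.** In section 3.7, replace Student's unpaired t-test with Welch's t-test for unpaired comparisons of means. State that linear regressions containing both cohorts will use heteroscedasticity-robust standard errors, for example HC3. State also that matched analyses will apply the matching weights and use standard errors clustered on matched set, allowing for reused controls, instead of Welch or plain HC3.

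This takes one or two sentences and a software option, with no new data. The only statistical price is slightly wider intervals when the SDs are in fact equal: about 0.14% at 770 vs 25,000 and about 1.1% at 77 vs 693. Section 4 reports that the register and record data are still being prepared for merging, so the choice can be fixed before the merged outcomes are analysed.

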To ensure optimal use of CSII and/or CGM, it is recommended that people with type 1 diabetes receive structured and recurring education (6, 7, 9). Yet, there is currently no consensus on which educational practice is best for a given patient (9, 10), and the literature indicates a paucity of high quality comparative studies regarding the effectiveness of technology-specific education (11, 12). Studies involving technology-specific education have shown that people with type 1 diabetes treated with CSII often do not use advanced pump functions or benefit substantially (13-15). These observations are concerning, particularly when combined with findings that using advanced functions can lead to improved HbA1c (16-19). It is frequently found that device-specific satisfaction is a good predictor of device utilization (20-23); however, preferences for device properties have seldomly been investigated or linked to outcomes and treatment goals of the individual (24). Whereas research mostly has focused on device-specific preferences and satisfaction (20-24), only little research has been conducted into individuals' needs and preferences for technology-specific education (12). However, meeting the needs and integrating the preferences of the individual in new interventions is considered integral to ensuring patient-centered and effective care (25-27). Accordingly, taking the target group's needs and preferences into account is essential to developing effective educational strategies (11, 25).

There are other barriers to treatment success than acquiring and maintaining the necessary skills to successfully manage CSII. For example, factors such as age and baseline HbA1c at treatment initiation have been identified as important predictors of treatment success in CSII-users (28-33).

Only a modest amount of literature has examined how psychosocial factors predict success (34, 35), with one study finding that psychological determinants, especially self-efficacy and locus of control, account for 50% of observed variation in HbA1c in people with type 1 diabetes using CSII (34). Likewise, an important known psychosocial predictor of poor diabetes outcomes is diabetes distress. One study found that a high level of diabetes distress was associated with higher HbA1c and less time in range compared to moderate or low levels of diabetes distress in people with type 1 diabetes using CSII; however, the high diabetes distress group did not perform less pump-specific

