self-management activities (e.g., use of bolus wizard) suggesting that other mechanisms than technology-specific behavior may drive differences in outcomes (36). Thus, alongside demographic, socioeconomic and health status factors, psychological and psychosocial predictors may play a significant yet underexplored part in the successful use of diabetes technology.

2. Aim

The present study is part of an overarching study being conducted in Denmark at Steno Diabetes Center Copenhagen (SDCC) and Nordsjællands Hospital Hillerød (NOH), Steno Tech, that aims to develop and ultimately, in a randomized controlled trial (RCT), test approaches that can assist people with type 1 diabetes in obtaining optimal outcomes using CSII. Through a large-scale, questionnaire-based online survey enriched with data from national registers, this sub-study contributes to this overarching aim by exploring the importance of individual differences across a wide range of factors, including demographic, socioeconomic, health status, psychosocial and preference structures, for optimal use of CSII in people with type 1 diabetes.

3. Methods

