3.3 Survey recruitment procedure

Beginning in quarter 3 of 2019, eligible survey participants were approached by their primary HCP in conjunction with a consultation at SDCC or NOH and invited to participate in the survey. If they agreed to participate, they received, upon survey-opening, an invitation in e-Boks¹ with a link to the survey and a standardized, mandatory document containing information on how their data would be stored and used. Before answering the survey, participants were prompted to provide written consent.

[figure not shown]
¹ e-Boks is an electronic mailbox designed to provide a digital and secure communication path between Danish citizens, companies and public authorities. As of quarter 2 of 2019, 91.5% of all Danish citizens have an e-Boks.

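### Does the plan need a rule ordering HbA1c against the survey answer, and a prior-HbA1c term, before it models HbA1c on survey scores?

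*Combined protocol and SAP*

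**What the plan says.** Section 3.7 (Data analysis) sets out a linear model as the general form, says that details will depend on the objective, and offers HbA1c only as an example of Y. It explains that the coefficient "is the effect on Y_i given X_n" and that X_n "indicates demographic, socioeconomic, behavioral and psychosocial factors". No earlier HbA1c is listed.

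Section 3.6 (Register and EMR data) states: "Register-extracted outcomes include all blood and urine test measures taken at the annual" check-up, HbA1c among them. It gives no year, window or order relative to the survey. Its one time window belongs to a different variable: "all encounters with the health care system in the survey period". On status it says: "A data extraction agreement with Statistics Denmark has been made and is currently being processed".

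Two other places bear on the point. The introductory text before section 2 says that age and "baseline HbA1c at treatment initiation have been identified as important predictors of treatment success in CSII-users". Section 2 (Aim) sets out to explore individual differences across many factors, "including demographic, socioeconomic, health status, psychosocial and preference structures". Section 4 dates the survey from 15 May to 15 October 2020, with 770 respondents.

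**The concern.** Several survey scores have short recall. In Appendix 1, hypoglycemia fear, diabetes distress and support ask about the past month, and WHO-5 about the past two weeks. An HbA1c measured before those windows cannot be a result of what the scores capture, yet section 3.6 allows it to serve as the outcome. The reverse direction is plausible from the items themselves: one distress item is about discouragement at unexplained high glucose readings, and high HbA1c is a listed reason for having been offered a sensor. A model without prior HbA1c, with coefficients described as effects, could present earlier control as a consequence of distress or of device choice. The sub-study informs approaches to be tested in a later randomised trial, so direction matters when choosing what to target.

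There is also a mismatch of lists. The Aim names health status and preference structures; the X_n list names neither.

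**Working it through.** The plan states no figure on this point, so there is none to reproduce. The check has three parts.

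**1. Text.** Comparing the Aim's five domains with the four in X_n leaves exactly two unnamed: health status and preference structures. X_n adds one, behavioral. Both unnamed domains are collected (Table 1 and Appendix 1: the health status VAS, and the risk, lottery and time-preference items), so the gap is in a descriptive sentence and not in the data. On timing, section 3.6 neither orders HbA1c relative to the answer nor says that test dates will be dropped. It extracts all annual check-up measures, so an earlier HbA1c is not excluded.

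**2. Could reverse association mislead?** Assume no forward effect, n = 770, a score–HbA1c correlation g of 0.1–0.3 and an HbA1c–HbA1c correlation ρ of 0.5–0.8. None of these correlations is in the documents. If HbA1c follows the answer and no prior value is in the model, the standardised slope is ρg, from 0.5 × 0.1 = 0.05 to 0.8 × 0.3 = 0.24. It is significant at two-sided 5% in about 28% to 100% of studies. The worry is therefore sound in principle.

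**3. Would the stricter analysis cure it?** Write r for the score–HbA1c correlation (0.1–0.3), s for the correlation between two HbA1c values (0.6–0.8), and p for the share of HbA1c values that precede the answer.

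*Ordering alone, if the last HbA1c drives the score.* The mixed-date association is r(p + (1−p)s) and the ordered one is rs, so the cut is 1 − s/(p + (1−p)s).

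- Illustrative p, assuming one check-up per person spread evenly over calendar 2020: 135/366 = 0.369 if everyone answers on 15 May, and 288/366 = 0.787 if everyone answers on 15 October.
- p = 0.369, s = 0.8: 1 − 0.8/0.874 = 8%.
- p = 0.787, s = 0.6: 1 − 0.6/0.915 = 34%.
- Bound without the calendar assumption (p = 1): 1 − s, or 20–40%.

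*Ordering alone, if the long-term level drives the score.* Both HbA1c values correlate r with the score, so the cut is 0%.

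*Adding the last pre-survey HbA1c.* If that value drives the score, the adjusted coefficient is 0, a 100% cut. If the long-term level drives it, the coefficient is r(1−s)/(1−r²):

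- r = 0.3, s = 0.6: 0.12/0.91 = 0.132, a cut of 56%.
- r = 0.1, s = 0.8: 0.02/0.99 = 0.020, a cut of 80%.

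A stable trait that truly affects HbA1c equally at both times produces the same correlations, so the adjusted model removes the same 56–80% of a real effect.

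*False signals that remain after adjustment (long-term level, no forward effect).* At r = 0.2 and s = 0.6 the partial correlation is 0.08/√(0.96 × 0.64) = 0.102. With n = 770 the test statistic centres near 0.102 × √770/√(1 − 0.102²) = 2.85, giving rejection in about 81% of studies. Across r 0.1–0.3 and s 0.6–0.8 the same formula gives 15% to 99%; simulation agrees to within about a percentage point.

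*Cost.* Under the same calendar-2020 assumption, respondents with a post-answer check-up number 770 × (1−p), from 164 to 486. The correlation detectable with 80% power (Fisher z, two-sided 5%) rises from 0.101 at n = 770 to 0.127 at 486 and 0.217 at 164. Avoiding that loss means a longer extraction window.

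**The case for a change.** The strongest case for a change is that no other text supplies the order or the covariates. Matching and paired t-tests appear in section 3.7 without matching variables or time points. The section also mentions quasi-experimental procedures, which makes the word effect less innocent. And because the extraction was still in process, keeping test dates would have been cheap then, whereas dates not retained may be hard to recover.

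Part of this stands. An index date is not written down, and for short-recall scores association is the accurate word. Three things limit it.

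- The coefficient gloss explains a symbol in a template; it is not a commitment on how results will be reported.
- The introductory text on baseline HbA1c concerns the value at treatment initiation, which is a different variable from the last value before the survey. It does not show that a required adjuster is missing.
- For anyone already on a sensor before the earlier test, that HbA1c comes after the exposure, and adjusting for it may remove a real effect. The sensor example is confounding by indication at the first offer, and the survey already records the reasons for that offer.

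Order alone is also weaker than it looks. Appendix 1 itself describes HbA1c as long-term blood glucose, so a test soon after the answer can still reflect glucose from before it.

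**Conclusion.** No change to the plan follows. The timing point is an unwritten detail in a generic, exploratory model, and analysts holding dated tests and survey completion dates would be expected to state the gap between them and describe the results as associations. A mandatory post-answer outcome or a prior-HbA1c model is a trade-off and not a clear gain. Ordering removes 0–34% of a reverse association in the illustration. Adjustment may remove 56–80% of a real stable-trait effect and cannot separate it from reverse causation. A post-answer outcome costs sample or a longer extract. The two domains absent from X_n are collected and named in the Aim, so their omission is a slip of wording.

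The percentages rest on assumed correlations, and the 34% and the sample counts also on an assumed even calendar-2020 spread of check-ups; they show scale only. The conclusion rests on the text: nothing in it fixes a wrong order, excludes an earlier HbA1c or discards dates. It would be different if the plan committed to causal claims from short-recall scores, or if test dates were not kept.
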